#### 6.2.6.1. Time to and Duration of ADA and nAb response

The ADA and nAb analyses described below will include patients with treatment-induced ADA or nAb, respectively.

Time (weeks) to ADA response is defined as:

$$(\text{Date of first positive ADA result} - \text{date of first dose of avelumab} + 1)/7.$$

Time to ADA response will be summarized using simple descriptive statistics (mean, SD, median, min, max, Q1, Q3).

Duration (weeks) of ADA response is defined as:

$$(\text{Date of last positive ADA result} - \text{date of first positive ADA result} + 1)/7.$$

Duration of ADA response will be censored if:

- the last ADA assessment is positive AND patient is ongoing treatment with avelumab, or

- the last ADA assessment is positive AND patient discontinued treatment with avelumab AND the last planned ADA assessment (day 30 follow-up visit) is after the cut-off date.

Time to nAb response and duration of nAb response are defined similarly based on first and last positive nAb result.

Kaplan-Meier estimates (product-limit estimates) will be presented together with a summary of associated statistics including the median ADA response time with 2-sided 95% CIs. ADA response rates at different timepoints will be estimated with corresponding 2-sided 95% CIs. The CIs for the median will be calculated according to Brookmeyer and Crowley (1982) and the CIs for the survival function estimates will be derived using the log-log transformation according to Kalbfleisch and Prentice (2011) (conftype=loglog default option in SAS Proc LIFETEST) with back transformation to a CI on the untransformed scale. The estimate of the standard error will be computed using Greenwood's formula.

Duration of ADA response will be displayed graphically and analyzed using Kaplan-Meier methodology. If the number of patients with ADA response is small, the Kaplan-Meier method may not provide reliable estimates. In this case, only descriptive statistics or listings will be provided

As data permit, the analyses described above will be repeated for patients with treatment-induced nAb.

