**Table 7 Patients Characterized Based on Anti-Drug Antibody Results (ADA Status)**

Category	Definition	Subjects at Risk (Denominator for Incidence)
ADA never-positive	No positive ADA results at any time point; ADA-negative patients (titer < cutpoint)	Number of patients with at least one valid ADA result at any time point
ADA ever-positive	At least one positive ADA result at any time point; ADA-positive patients (titer ≥ cutpoint)	Number of patients with at least one valid ADA result at any time point
Baseline ADA positive	A positive ADA result at baseline	Number of patients with valid baseline ADA result
Treatment-boosted ADA	A positive ADA result at baseline and the titer ≥ 8×baseline titer at least once after treatment with avelumab	Number of patients with valid baseline ADA results and at least one valid post-baseline ADA result
Treatment-induced ADA	Patient is ADA-negative at baseline and has at least one positive post-baseline ADA result; or if patient does not have a baseline sample, the patient has at least one positive past-baseline ADA result	Number of patients with at least one valid post-baseline ADA result and without positive baseline ADA result (including missing, NR)
Transient ADA response	If patients with treatment-induced ADA have (a single positive ADA result or duration between first and last positive result <16 weeks) and ADA result at the last assessment is not positive.	Number of patients with at least one valid post-baseline ADA result and without positive baseline ADA result (including missing, NR)
Persistent ADA response	If patients with treatment-induced ADA have duration between first and last positive ADA result ≥16 weeks or a positive ADA result at the last assessment	Number of patients with at least one valid post-baseline ADA result and without positive baseline ADA result (including missing, NR)

ADA: anti-drug antibody, NR = not reportable.

Patients will be characterized into different nAb categories based on the criteria in [Table 8](#). For nAb, treatment-boosted is not applicable since no titer result is available.

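### SAP 6.2.6.1: a patient off avelumab and still ADA-positive at the last sample becomes a Kaplan-Meier event, so ADA persistence is estimated too short or, at best, unchanged

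*SAP*

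**What the plan says.** SAP 6.2.6.1 restricts the analysis to treatment-induced cases: "The ADA and nAb analyses described below will include patients with treatment-induced ADA or nAb, respectively". The duration ends at the "Date of last positive ADA result"; first and last positive dates are subtracted, one day is added, and the result is divided by 7 to give weeks. The method is stated: "Duration of ADA response will be displayed graphically and analyzed using Kaplan-Meier methodology".

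The censoring rule opens with "Duration of ADA response will be censored if" and lists two cases:

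- "the last ADA assessment is positive AND patient is ongoing treatment with avelumab, or"
- last assessment positive, patient off avelumab, "AND the last planned ADA assessment (day 30 follow-up visit) is after the cut-off date".

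No other censoring is provided for. SAP 6.2.6 makes the Day 30 follow-up visit the last ADA sample, after pre-dose samples at Cycles 1, 2, 3, 4, 6 and 8 and then about every 12 weeks. SAP 5.2.1 excludes data after the cut-off.

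Table 7 defines a persistent response as a span of at least 16 weeks between first and last positive, or "a positive ADA result at the last assessment". Durations for nAb are defined in the same way as for ADA.

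**The concern.** In a Kaplan-Meier analysis a time that is not censored is an event. The SAP does not use the word event here, but no other reading fits the method. For a patient who has stopped avelumab and was positive at Day 30, the response is therefore recorded as ending on a day when ADA was present, and no later sample is planned that could show its loss. The same happens to a patient who missed a Day 30 visit planned on or before the cut-off and was positive at the previous sample.

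Immunogenicity of avelumab in the combination is a stated secondary objective. A reader of the report will take a Kaplan-Meier median ADA duration as a statement about how long antibodies last. To the extent that still-positive patients are coded as events, it describes instead when sampling stopped. The nAb analysis would follow the same rule if the assay becomes available; it was not available when the SAP was finalised.

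**Working it through.** **1. Which patients are affected.** All patients below have a positive last ADA result.

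| Status at cut-off | Rule met | Coded as |
|---|---|---|
| On avelumab | first | censored |
| Off avelumab, planned Day 30 visit after cut-off | second | censored |
| Off avelumab, planned Day 30 visit on or before cut-off | neither | event at last positive |

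The third row is the gap. At the primary cut-off (78 weeks after the last patient's first dose, SAP 2) some patients may still fall in the first two rows. At the final analysis, after last patient last visit, almost none can.

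**2. Conflict with Table 7.** Take a patient whose first positive result is the Day 30 sample. Duration = (0 + 1)/7 = 0.14 weeks, coded as an ended response. Table 7 calls the same patient persistent, because the last assessment is positive.

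**3. Direction.** At each event time the Kaplan-Meier curve is multiplied by 1 − d/n, where d is the number of events and n the number at risk. Recoding a censored time as an event leaves every n unchanged and can only increase a d. The curve is lower or equal at every time, and so are the median and the rates.

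**4. Small example (all durations assumed).** Four patients reverted, with last-positive durations of 2.1, 4.1, 8.1 and 12.1 weeks. Four were off avelumab and positive at Day 30, with durations of 6.1, 10.1, 18.1 and 30.1 weeks. The median is taken as the first time the curve is at or below 0.5.

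- SAP rule, all eight are events: the curve falls by 1/8 at each time and reaches 4/8 = 0.50 at 8.1 weeks. Median 8.1. At 24 weeks one of eight remains: 0.125.
- Last-positive patients censored: 7/8 = 0.875 at 2.1; × 6/7 = 0.75 at 4.1; × 4/5 = 0.60 at 8.1; × 2/3 = 0.40 at 12.1. Median 12.1. At 24 weeks: 0.40.

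**5. Simulation on the SAP schedule (hypothetical).** Assumed: ADA onset uniform over weeks 1 to 14, exponential ADA duration, exponential time on avelumab with a 2-week minimum, and samples at weeks 2, 4, 6, 10, 14, 26 and every 12 weeks while on treatment, plus one sample 30 days after stopping. There were 8,000 simulated patients per row, all off treatment with Day 30 done, as at a final analysis. The protocol's end of on-treatment ADA sampling at Cycle 50 was not applied. Shortfall = 1 − (SAP-rule median / median with censoring).

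| True median ADA duration (wk) | Median time on avelumab (wk) | Positive at last sample | SAP-rule median (wk) | Median with censoring (wk) | Shortfall |
|---|---|---|---|---|---|
| 12 | 26 | 33% | 4.14 | 8.14 | 49% |
| 12 | 52 | 20% | 5.34 | 8.14 | 34% |
| 26 | 26 | 53% | 10.14 | 24.14 | 58% |
| 26 | 52 | 35% | 12.14 | 24.14 | 50% |
| 52 | 26 | 69% | 15.29 | 56.14 | 73% |
| 52 | 52 | 52% | 22.49 | 52.14 | 57% |

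The SAP states no figure on this point, so there is nothing of its own to reproduce.

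**The case against.** The strongest defence is that the SAP defines duration as the span between first and last positive results, not as time to loss of ADA. Both censoring conditions describe patients with a planned sample still to come; once the last planned sample is taken, the span is complete. On this view nothing is biased. Table 7 only assigns a category and sets no end date.

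This does not rescue the analysis. The SAP never states that target, and censoring still-positive patients on treatment points to an interest in how long the response really lasts. A summary of the observed span already exists: the cross-tabulation of duration and titre in SAP 6.2.6.2 says that censoring is ignored there. For duration of tumour response (SAP 6.2.2.3), a patient without progression or death is censored at the last adequate assessment. It does stand that the bias is a bias with respect to persistence, and that the Table 7 counts give some information on persistence outside the Kaplan-Meier result, without correcting it.

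The other objection is materiality. No hypothesis test is planned, at most about 55 patients are expected, and only those with treatment-induced ADA enter. The SAP also has a fallback: "If the number of patients with ADA response is small, the Kaplan-Meier method may not provide reliable estimates", in which case only descriptive statistics or listings are given. This stands, and keeps the point minor.

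**Conclusion.** The censoring rule is wrong as written, with low materiality. For a patient off avelumab, with the planned Day 30 visit on or before the cut-off and a positive last result, it records an end of response that was not observed. As an estimate of ADA persistence, the curve, median and rates are short or unchanged. The direction is certain; it rests only on reading uncensored as event. The size cannot be found from the documents. The simulated shortfalls of 34% to 73% depend on assumed durations and put every patient off treatment.

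Three stronger readings are tempting and not supported:

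- A reader might infer that the longest responses in general are treated as ended. Still-positive patients on avelumab, or with Day 30 after the cut-off, are censored already, and the gap also catches very short spans such as the 0.14 weeks above.
- A reader might infer that the median reflects length of sampling more than persistence. That depends on the proportion of patients in the gap, which is unknown.
- A reader might attach a definite size, for example a true median of 20 weeks reported as 14, or 40 as 20. Those figures need every patient off treatment, loss of ADA observed continuously, and sampling that ends 4 to 60 weeks after the first positive. None of this comes from the documents.

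**What to change.** Replace the two censoring conditions in SAP 6.2.6.1 with one: censor at the date of the last positive result whenever the last valid ADA result on or before the cut-off is positive, whatever the treatment status or Day 30 timing, and count an event only when a later valid negative result exists. Apply the same rule to nAb if it is assayed.

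The cost is one SAP sentence and a change to the event flag; no new data are needed. The median may be reported as not reached, which would be the honest result.

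The change does not remove all error. Dating the end at the last positive sample still pulls duration down somewhat, because samples are up to about 12 weeks apart. In the simulation the censored medians were 8.14 against a true 12 weeks, 24.14 against 26, and 52.14 to 56.14 against 52, so the remaining error was not always downward. A footnote giving the sampling interval would be enough.

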#### **6.2.6.2. ADA titer**

For patients who are ADA ever positive, the maximum observed ADA titer for a patient will be summarized, overall and by ADA subcategories (baseline ADA positive, treatment-boosted ADA, treatment-induced ADA, transient ADA response, persistent ADA response) of patients having each discrete maximum titer value will be tabulated. The denominator to calculate the percentages will be the total number of patients in the associated ADA subcategory.

For patients with treatment-induced ADA, a cross tabulation of duration of ADA response and maximum ADA titer will be provided. The following categories for duration of ADA response will be used:  $\leq 1$ ,  $>1$  to  $\leq 3$ ,  $>3$  to  $\leq 5$ ,  $>5$  to  $\leq 7$ ,  $>7$  to  $\leq 13$ ,  $>13$  to  $\leq 16$ ,  $>16$  to  $\leq 25$ ,  $>25$  weeks. In this categorization, the censoring in duration of ADA response is ignored.

#### **6.2.6.3. Analysis of PK, safety and efficacy by immunogenicity status**

The following ADA and nAb status will be used for the analyses described below.

ADA

- ADA ever-positive versus ADA never-positive
- ADA: treatment-induced ADA versus ADA never-positive or baseline ADA positive

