### PK parameters and immunogenicity status

The following analyses will include patients in both the immunogenicity analysis set and in the PK parameter analysis set. The PK endpoints pertinent to the immunogenicity analyses are  $C_{\text{trough}}$  and  $C_{\text{max}}$ .

Blood samples for avelumab PK will be collected as outlined in the “Schedule for Pharmacokinetic Sample Collection” table of the Schedule of Assessments section of the protocol.

$C_{\text{trough}}$  and  $C_{\text{max}}$  will be summarized descriptively (n, mean, SD, CV, median, minimum, maximum, geometric mean, its associated CV, and 95% CI) by nominal time and ADA status. Linear-linear and log-linear plots of mean and median for  $C_{\text{trough}}$  and  $C_{\text{max}}$  over nominal time and by ADA status will be presented.

Among patients with treatment-induced ADA, analyses will be conducted to assess whether  $C_{\text{trough}}$  and  $C_{\text{max}}$  have any changes before and after the first positive ADA assessment. To be included in this analysis, patients must have the same PK parameter available both before and after the first positive ADA assessment. Relative PK day will be calculated as:

$$(\text{PK assessment nominal day}) - (\text{first positive ADA assessment nominal day}).$$

Nominal day is the protocol scheduled timing for an assessment. For example, if  $C_{\text{trough}}$  is collected on Day 1 of Cycle 2 and the first positive ADA result is observed on Day 1 of Cycle 3, then the relative PK day for this  $C_{\text{trough}}$  is -14. Linear-linear and log-linear plots of mean and median for  $C_{\text{trough}}$  and  $C_{\text{max}}$  over relative PK day will be presented.

As data permit, the analyses described above will be repeated for nAb.

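### Neither ADA-status contrast in SAP 6.2.6.3 separates ADA caused by treatment (induced or boosted) from pre-existing or absent ADA

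*SAP*

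**What the plan says.** SAP 6.2.6.3 names the groups first: "The following ADA and nAb status will be used for the analyses described below". For ADA there are two contrasts:

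- "ADA ever-positive versus ADA never-positive"
- "ADA: treatment-induced ADA versus ADA never-positive or baseline ADA positive"

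The PK part of that section then summarizes avelumab Ctrough and Cmax "by nominal time and ADA status", and the safety part tabulates treatment-emergent adverse events by ADA status.

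The categories come from SAP Table 7. Treatment-boosted ADA is "A positive ADA result at baseline and the titer ≥ 8×baseline titer at least once after treatment with avelumab". Treatment-induced ADA applies when "Patient is ADA-negative at baseline and has at least one positive post-baseline ADA result", or when the baseline sample is missing and a later result is positive. For the boosted row, the column of subjects at risk reads "Number of patients with valid baseline ADA results and at least one valid post-baseline ADA result". For the induced row, the same column leaves out patients with a positive baseline result.

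**The concern.** By its own definitions the SAP treats a titer rise of 8-fold or more on avelumab as a response to treatment. When it relates ADA to exposure and adverse events, however, patients with such a rise stand on the reference side of the only contrast built around treatment-induced ADA. Any low trough concentration or adverse event in a boosted patient is then shown under the group meant to have no treatment response.

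At stake is a small index group that loses some of its responders, and a reference group that contains a few of them. There is also a smaller point in Table 7. The boosted percentage is taken over a group that includes baseline-negative patients, who cannot be boosted. The induced row does remove the patients who cannot be induced.

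**Working it through.** The main point concerns group definitions, and the plan gives no figure to reproduce. In what follows, treatment-caused is shorthand for induced or boosted as Table 7 defines them.

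**Step 1: place each ADA pattern (Table 7) in the two contrasts (6.2.6.3).**

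| Baseline / post-baseline | Contrast 1 (ever vs never) | Contrast 2 (induced vs never or baseline positive) | Treatment-caused? |
|---|---|---|---|
| negative / negative | reference | reference | no |
| negative or missing / positive | index | index | yes (induced) |
| positive / titer at least 8 × baseline | index | **reference** | **yes (boosted)** |
| positive / positive, below 8 × baseline | index | reference | no |
| positive / negative | index | reference | no |

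The treatment-caused set is rows 2 and 3. The index group is rows 2 to 5 in contrast 1 and row 2 alone in contrast 2. Neither matches.

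**Step 2: look for another analysis that fills the gap.**

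- The within-patient comparison of Ctrough and Cmax before and after the first positive result (6.2.6.3, PK part) is limited to treatment-induced patients.
- Time to ADA response and its duration (6.2.6.1) are also limited to treatment-induced patients.
- Boosted patients appear as a group only in the Table 7 incidence and in the maximum-titer summary (6.2.6.2).

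No visible analysis relates boosted ADA to PK or safety.

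**Step 3: size.** The documents give no ADA rates, so these are assumptions: baseline positivity b = 2% to 10%, fraction of those boosted f = 10% to 50%, treatment-induced ADA i = 5% to 25% of patients. N = 55 is the approximate maximum enrolment in SAP 5.1.1, and every patient is taken to have usable ADA data.

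- Expected boosted = N × b × f. Low: 55 × 0.02 × 0.10 = 0.11. High: 55 × 0.10 × 0.50 = 2.75.
- Share of the contrast 2 reference group = boosted / (N − N × i). Low: 0.11 / 52.25 = 0.2%. High: 2.75 / 41.25 = 6.7%.
- Share of treatment-caused responses that sit in the reference = boosted / (boosted + N × i). Low: 0.11 / (0.11 + 13.75) = 0.8%. High: 2.75 / (2.75 + 2.75) = 50%.
- Chance of at least one boosted patient = 1 − (1 − b × f)^55. Low: 1 − 0.998^55 = 10%. High: 1 − 0.95^55 = 94%.
- In contrast 1, unboosted baseline positives as a share of ever-positives = N × b × (1 − f) / (N × b + N × i). Low: 0.55 / (1.1 + 13.75) = 4%. High: 4.95 / (5.5 + 2.75) = 60%.

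**Step 4: the Table 7 denominator.** Suppose 52 evaluable patients, 4 of them baseline positive and 2 of those boosted. The boosted row reports 2/52 = 3.8%. Among the patients who could be boosted it is 2/4 = 50%.

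**The case against.** A reader might infer that no planned comparison isolates an antibody response to treatment. The documents do not support that. The before-and-after PK analysis uses each treatment-induced patient as their own control, so boosted patients cannot contaminate it. The index side of contrast 2 is likewise purely de novo. What remains is that both leave boosted patients out.

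A reader might also infer that the immunogenicity objective is undermined. As stated (SAP 2.1), it is only to assess the immunogenicity of avelumab given with axitinib. Table 7 and the titer summary report boosted ADA for that purpose. The link to PK and safety comes from 6.2.6.3, which is supplementary and descriptive.

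The numerical case for leaving the plan alone is fair. SAP 5.1.1 plans no formal hypothesis testing, few boosted patients are likely, and 6.2.6.3 promises listings of immunogenicity data alongside PK, safety and efficacy, so individual boosted patients can be inspected. The Table 7 denominator is stated openly, and the baseline-positive count appears in the same table. These arguments bear on how much the point matters; they do not change the grouping.

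Replacing contrast 2 would lose the de novo comparison and its parallel with nAb, for which no boosted category exists because there is no titer. That argues for adding a contrast and keeping the present ones.

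Finally, the safety list is redacted after two items and no efficacy text is visible. Step 2 therefore speaks only of visible analyses, although the status definitions stand ahead of all of them.

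**Conclusion.** The point holds as a matter of definition: boosted patients are in the reference group of the second contrast, and in the first they are pooled with unchanged baseline positives. It applies to ADA only.

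The expected effect is small. On the assumed rates fewer than 3 boosted patients are expected, at most 6.7% of the reference group. The larger share is on the other side: up to half of all treatment-caused responses could be missing from the index group, at the extreme of 10% baseline positivity, half of those boosted, and only 5% induced. All of these figures rest on assumed rates, and with no boosted patient they are all zero.

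It would be tempting to add that the comparison loses precision or is materially biased. Assume 52 patients with 4 induced, 1 to 4 boosted, and a 60% CV. The standard error of a log Ctrough ratio would then be 11% to 35% wider than with boosted patients moved to the index group, and a true halving would read as 0.51 to 0.53. The SAP plans no such ratio or test, however, so the widening describes no planned output, and the shift is slight even in the illustration. The reason to act is that the grouping conflicts with the SAP's own definitions and is cheap to correct before ADA results are seen.

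**What to change.** Keep both contrasts in SAP 6.2.6.3 and add a third for ADA: treatment-induced or treatment-boosted ADA against ADA never-positive or baseline-positive without a boost, among patients with at least one valid post-baseline ADA result. That restriction is needed because Table 7 lets a patient count as never-positive on a single valid result at any time. A patient with only a negative baseline sample would otherwise enter the reference with no chance to show a response.

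At minimum, take boosted patients out of the reference of the second contrast and show them as a separate group.

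As a secondary change, also report the boosted percentage in Table 7 among patients with a positive baseline ADA result and at least one valid post-baseline result.

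The cost is one derived flag, one extra set of small tables, and the lack of a matching nAb contrast. No new data are needed: SAP 6.2.6 already has ADA-positive samples analysed for titer.
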